## 6. STATISTICAL METHODS

### 6.1. Analysis of demographics (for each of the four groups of the study)

#### 6.1.1. Analysis of demographics planned in the protocol.

Except when specified otherwise, summary by age strata (**50-59, 60-69, and  $\geq 70$  YOA**) will be set up as per the age at the first vaccination in the ZOSTER-006/022 studies.

Demographic characteristics (age at first vaccination in the ZOSTER-006/022 studies, **age at enrolment in ZOSTER-049**, gender, race, region, and ethnicity), cohort description and withdrawal status will be summarized.

For LTFU group, mean age at first vaccination in the ZOSTER-006/022 and mean **age at enrolment in ZOSTER-049** studies (plus range and standard deviation) of the enrolled subjects, as a whole, and stratified by **age strata (50-59, 60-69 ≥70 and ≥60 YOA at primary vaccination)** will be calculated on TVC, ATP cohort for humoral persistence – LTFU, ATP cohort for CMI persistence – LTFU at baseline.

In addition, for the 1-Additional Dose, Revaccination and Control groups, **mean age at first vaccination in the ZOSTER-006/022 and** mean age at Month 0 in the ZOSTER-049 (plus range and standard deviation) of the enrolled subjects **on TVC - Randomized groups**, and **ATP cohort for immunogenicity – Randomized groups** as a whole will be calculated.

The distribution of subjects enrolled among the study sites **from different countries** will be tabulated.

**Descriptive statistics of interval (in years)** between the end of study efficacy cut-off date (21 April 2015) of ZOSTER-006/022 and the first visit of the LTFU and control group will be calculated overall and by age strata (**50-59, 60-69, 70-79, ≥80 YOA at primary vaccination**) **on mTVC - LTFU and Control group**.

**Descriptive statistics of interval (in years)** between the second dose of HZ/su vaccine in ZOSTER-006/022 and the first dose in the Revaccination group and the 1-Additional Dose group and the first visit for the control group will be calculated overall **on TVC – Randomised groups**.

**Descriptive statistics of interval (in years)** between the second dose of HZ/su vaccine in ZOSTER-006/022 and the first visit for the control group **and LTFU** will be calculated overall and by age strata (**50-59, 60-69, 70-79, ≥80 YOA at primary vaccination**) **on mTVC - LTFU and Control group**.

**Descriptive statistics of interval (in years) between the second dose of HZ/su vaccine in ZOSTER- 006/022 and Year 6 visit for the LTFU and Control will be calculated overall and by age strata (50-59, 60-69, 70-79, ≥80 YOA at primary vaccination) on mTVC - LTFU and Control group.**

**Frequency and percentage will be generated for categorical variables such as gender, race, region, and ethnicity.**

#### 6.1.2. Additional consideration

**Following CHMP recommendation, in order to evaluate the comparability of demographic characteristics between subjects enrolled in ZOSTER-049 and subjects enrolled in ZOSTER-006/022 studies, demographic characteristics of age, gender, race, region and ethnicity will also be summarized for subjects enrolled in ZOSTER-049, and subjects receiving at least one dose of HZ/su vaccine in ZOSTER-006/022 studies. In addition, selected medical conditions present at enrolment of ZOSTER-049 will be summarized.**

**Summary of demography will also be performed by age-strata (50-59, 60-69, 70-79, ≥80, ≥60, ≥70 YOA at primary vaccination), gender, region, race and ethnicity on mTVC -LTFU and Control group.**

## 6.2. Analysis of efficacy (LTFU and Control group)

### 6.2.1. Analysis of efficacy planned in the protocol (LTFU and Control group)

The efficacy analyses are summarized by age strata and overall as presented in the [Table 1](#). The calculations involving ZOSTER-049 only will consider data collected only in the present study follow-up. The calculations involving ZOSTER-006/022 and ZOSTER-049 will combine results from the studies as described below.

**Table 1 Efficacy analyses per study periods and age-strata**

Analysis	Study period	≥ 50 YOA	≥ 60 YOA	≥ 70 YOA	50-59 YOA	60-69 YOA	70-79 YOA	≥ 80 YOA	Objective
A	Z-049 duration overall	X	X	X	X	X	X	X	Primary and Secondary
B	Z-006/Z022 * + Z049 duration overall	X	X	X	X	X	X	X	Secondary
C	Z-006/022 + Z-049 duration yearly**	X	X	X	X	X	X	X	Secondary and CCI

YOA = Year of age

\* from one month post dose 2 in the ZOSTER-006/022 studies

\*\* yearly follow-up will be computed from one month post dose 2 in the ZOSTER-006/022 studies. Note that results from the pooled ZOSTER-006/022 studies will be presented for each year after vaccination with methods used in these studies.

The primary analysis of efficacy will be performed on the mTVC, the analysis will be also performed on the TVC for efficacy and the ATP for efficacy to complement the mTVC analysis.

The **VE analysis for HZ** on TVC, mTVC and ATP cohort for efficacy over the study duration of present study ZOSTER-049 will be performed over the follow-up time calculated from enrolment in the present study to the time of first confirmed HZ case for a subject with a confirmed HZ case, and to the date of last contact for subjects without the occurrence of confirmed HZ case.

The **VE analysis for HZ** on mTVC and ATP cohort for efficacy over the duration starting from ZOSTER-006/ -022 study will be performed over the follow-up time calculated from one month post Dose 2 to the time of first confirmed HZ case for a subject with a confirmed HZ case, and to the date of last contact for subjects without the occurrence of confirmed HZ case.

The **VE analysis for HZ** on the TVC will be performed over the complete follow-up period and will include confirmed HZ cases from Dose 1 administered in the ZOSTER-006/022 studies for vaccine efficacy evaluation. The end of the follow-up period will be calculated according to the same principle as will be done for the mTVC and ATP analyses for efficacy, i.e., up to the confirmed HZ case for a subject with a confirmed HZ case, or up to the date of last contact for subjects without a confirmed HZ case.

***In the VE analysis for PHN and HZ related complication (other than PHN), the follow-up time will be calculated in the similar way as in VE analysis for HZ.***

All above analyses will be performed overall and by age strata. The age strata for VE are defined as: **50-59, 60-69, 70-79, ≥80, ≥60, ≥70 YOA** at primary vaccination in ZOSTER-006/022 studies.

The primary analysis (A) will assess the VE during this study and will use the historical control estimates adjusted for region and age categories at randomization/vaccination during the ZOSTER-006/022 studies. Vaccine effects will be estimated by calculating the VE and estimating 95% CIs based on the variance of the observed population in this study and treating the historical control as constant, similarly, as described in [Morrison, 2015]. The secondary analysis C in [Table 1](#) will assess the VE over each year of follow-up, similarly to what is planned in analysis A.

See Section [7.3](#) for more details on the vaccine efficacy methodology.

The purpose of these analyses will be descriptive and therefore the CIs will not be adjusted for multiple testing.

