**CONFIDENTIAL**

201190 (ZOSTER-049 EXT:006-022)  
Protocol Amendment 5 Final

The primary analysis will be to assess the VE during this study and will use the historical control estimates adjusted for age at randomisation during the ZOSTER-006/022 studies. The method using the historical control estimates will be further explained in the Statistical Analysis Plan (SAP). Vaccine effects will be estimated by calculating the VE and estimating 95% CIs based on the variance of the observed population in this study and treating the historical control as constant.

The secondary analysis will be to assess the VE over each year of follow-up. Results from the ZOSTER-006/022 studies will be pooled for each year after vaccination with methods used in these studies. For overlapping years between ZOSTER-006/022 studies and this study, all the data will be pooled. For the non-overlapping years only the data from this ZOSTER-049 study will be used.

The assessment of the VE over the overall period including period from vaccination during the ZOSTER-006/022 studies up to the end of this long-term study will be done with a method that will be described in the SAP.

Any available information for the diagnosis of HZ episodes (clinical diagnosis, PCR, laboratory methods, etc.) during the interval between the end of the ZOSTER-006/022 studies and beginning of the ZOSTER-049 study is to be collected. Confirmation of all of these cases in the exact way as what will be done for cases collected during the clinical study follow-up periods of the ZOSTER-006, ZOSTER-022 and ZOSTER-049 will not be possible. Therefore, these cases will not be part of all efficacy analyses. A sensitivity analysis to assess the impact of these cases on the VE will be performed (this will be described in the SAP).

The purpose of these analyses will be descriptive and therefore the CIs will not be adjusted for multiple testing.

The analyses will be performed for confirmed HZ cases, for PHN and for complications (other than PHN).

Any exploratory or sensitivity analysis may be performed in addition to the analyses described above on an ad-hoc basis. However, the significance level of those analyses may not be fully controlled.

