### 7.3.3. Method for determining Historical Control Reference Group for Planned Analysis

The proposed model is specified prior to performing any interim analysis and is based on analysis performed on previous studies ZOSTER-006/022.

*Since there is no concurrent placebo group in ZOSTER-049, incidence rates estimations on the hypothetical Control group in ZOSTER-049 study are done by utilizing Poisson regression model using data from the Placebo group in ZOSTER-006/022 study to obtain the coefficients for region and by age strata (based on age on primary vaccination). The resulting estimated incidence rate adjusted for region and by age strata are then multiplied by the actual follow-up (FU) time observed in the ZOSTER-049 study (all vaccinated subjects) to obtain the estimated number of HZ cases on the hypothetical Control group. The same incidence rate estimates by region and by age strata will be used in both yearly and overall VE calculation.*

The statistical methodology used to estimate the incidence rate on the hypothetical ZOSTER-049 control from the historical control reference group is described below. The calculation of the vaccine efficacy is based on the methodologies used in the Merck paper (Morrison) and will be done stepwise as described below:

1. Poisson regression models are used to estimate the incidence rate for HZ for the ZOSTER-049 study hypothetical placebo group based on historical controls from ZOSTER-006/022 study:

A Poisson regression model based on placebo's HZ rates in ZOSTER-006/022 studies is developed for estimating the regression coefficient in each age strata (age at first vaccination in ZOSTER-006/022 studies): **50-59, 60-69, 70-79, ≥80, ≥ 60, ≥ 70 YOA.**

$$\text{Ln}(r_{\text{HZplacebo in zoster-006/022}}) = \alpha + \beta_{\text{Australasia}} * \text{RegionAustralasia} + \beta_{\text{Europe}} * \text{RegionEurope} + \beta_{\text{North America}} * \text{RegionNorth America} + \beta_{\text{Latin America}} * \text{RegionLatin America}$$

Where

- $\text{Exp}(\alpha)$  = mean HZ rate across all regions
- Region\_Australasia, Region\_Europe, Region\_North America, Region\_Latin America are indicator variable(1/0)
- $\beta_{\text{Australasia}}, \beta_{\text{Europe}}, \beta_{\text{North America}}, \beta_{\text{Latin America}}$ : estimated region-specific Poisson regression coefficients for HZ rate.

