#### **7.3.4. Method for computing VE and the associated CIs**

Once estimated data for the hypothetical control are generated as per steps listed in Section 7.3.2, following similar approach in ZOSTER-006/022, Poisson regression model will be used to estimate VEs and the associated CIs for all the planned VE analysis. Region will be included as a fixed effect and analysis will be performed on the following age strata ((50-59, 60-69, 70-79, ≥80, ≥60, ≥70 YOA) separately and overall.

*In the situation that there is no case in HZ/su group and >0 cases in Placebo group, VE and UL of VE will be set to be 100%. In the situation that there is >0 cases in HZ/su group and 0 case in Placebo group, VE and CI of VE will be set as “not available” (“-” or “U”).*

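### The Analysis A 95% CI for VE leaves out the sampling error of the estimated historical placebo rate and is slightly too narrow; SAP 7.3.4 does not say how the expected control cases enter the model

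*SAP*

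**What the plan says.** - **Variance rule.** For Analysis A (VE over ZOSTER-049, overall and by age stratum), SAP 6.2.1 prescribes "estimating 95% CIs based on the variance of the observed population in this study and treating the historical control as constant". Protocol 11.7.2 has the same clause, "treating the historical control as constant". SAP 6.2.1 cites a published long-term zoster vaccine study as precedent.
- **Where the control rate comes from.** SAP 7.3.3 fits a Poisson regression with region terms, within age stratum, to the ZOSTER-006/022 placebo data. The fitted rates are "multiplied by the actual follow-up (FU) time observed in the ZOSTER-049 study (all vaccinated subjects) to obtain the estimated number of HZ cases". It adds: "The same incidence rate estimates by region and by age strata will be used in both yearly and overall VE calculation".
- **How VE and its CI are computed.** SAP 7.3.4 says: "Poisson regression model will be used to estimate VEs and the associated CIs for all the planned VE analysis". It gives no variance formula and does not say whether expected cases are an offset or a second group of counts. It begins "Once estimated data for the hypothetical control are generated as per steps listed in Section 7.3.2", but 7.3.2 is the Bayesian section and the steps are in 7.3.3. For zero vaccine cases, its rule for "no case in HZ/su group and >0 cases in Placebo group, VE and UL of VE will be set to be 100" per cent fixes the estimate and the upper limit and names no method for the lower limit.
- **Safeguards.** SAP 7.3.1 warns that these estimates are not equivalent to VE from a controlled randomised study. SAP 7.3.2 describes a Bayesian analysis that would carry the control's uncertainty, but only as something that may be done. All analyses are descriptive, with no success criteria.

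**The concern.** The historical rate is an estimate. With P placebo cases behind it, log rate has a variance of roughly 1/P, and the rule in SAP 6.2.1 sets that to zero. The resulting interval describes VE relative to a fixed reference rate. Read as a 95% CI for VE itself, it is too short. Because the plan has no hypothesis test, the estimate and its interval are the result, so the label on the interval should be right.

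The silence in SAP 7.3.4 adds to this. A programmer could enter the expected cases as an offset, which follows 6.2.1, or as observed counts in a second group. The second choice adds variance 1/E, where E is the expected number of cases. E depends on vaccinee follow-up time, not on how much placebo data produced the rate, so that interval would contradict 6.2.1 and be too wide.

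**Working it through.** **1. The plan's own figures.** Protocol 11.4: 7344 × 0.50 = 3672; 13,500/2 × 0.90 = 6075, × 0.45 = 2734; total 6406. Protocol 11.4.1 removes the 240 randomised subjects (6166) and rounds to about 6000. It then states at least 99% probability that the lower limit of overall VE exceeds 30%. The VE and placebo rate behind that statement are not visible. In the least favourable setting used below (5/1000, 4 years, VE 65%) the probability is 99.84% under the constant rule, 99.67% with the control variance added and 99.31% with a two-group fit. The statement holds under all three.

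**2. Inputs.**
- Historical control (assumed): placebo arms equal in size to the HZ/su arms, 7344 + 6075 = 13,419, for about 4 years (protocol 1.2.1), giving 53,676 person-years.
- ZOSTER-049: 6000 subjects for 4-6 years. The design is about 6 years; the lower end allows for attrition (assumed).
- Control incidence: 5-10 per 1000 per year, the background range in protocol 1.1 (assumed for placebo).
- VE: 65% and 80%, from the titles of protocol Tables 29 and 30. Those tables are for yearly VE; the values are also applied overall (assumed).

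**3. Formulas.** P = 53,676 × incidence = 268-537. E = 6000 × years × incidence = 120-360. Expected vaccine cases x = (1 − VE) × E. Var(log RR) is:
- constant control: 1/x
- control uncertainty carried: 1/x + 1/P
- two-group fit to expected cases: 1/x + 1/E

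The ratio of the constant standard error to the one carrying both sources is 1/√(1 + x/P). Incidence cancels, and E/P runs from 24,000/53,676 = 0.447 to 36,000/53,676 = 0.671.
- VE 65%: 1/√(1 + 0.35 × 0.447) = 0.930, down to 0.900, so 7-10% too small.
- VE 80%: 0.958 down to 0.939, so 4-6% too small.

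**4. Example** (9/1000, 5.5 years, VE 65%): E = 297, P = 483, x = 104. Lower limit = 1 − 0.35 × exp(1.96 × SE): 57.6% constant, 56.7% with 1/P, 56.2% two-group.

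**5. Overall range for Analysis A** (400,000 Poisson draws of placebo and vaccine cases per setting):

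| | VE 65% | VE 80% |
|---|---|---|
| Constant control, Wald coverage | 92.2-93.3% | 93.5-94.2% |
| Constant control, exact interval coverage | 92.8-94.2% | 94.2-95.2% |
| With 1/P added, coverage | about 95% | about 95% |
| Lower limit too high by | 0.7-1.3 points | 0.3-0.6 points |

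**6. Age strata** (assumed shares of the example's P and E):
- 25% share (P = 121, E = 74): lower limit 48.6 against 46.5 at VE 65%, 66.7 against 65.7 at VE 80%.
- 10% share (P = 48, E = 30): 35.7 against 31.6, and 55.3 against 53.1.

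**7. One ZOSTER-049-only year** (E = 30-60, P unchanged): the constant rule covers about 95% or slightly more (94.9-96.5%). A two-group fit covers 97.2-98.2%, with a lower limit 2.0-6.6 points below the constant one.

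**8. Zero vaccine cases** (illustration, E = 15.4, constant control): the exact lower limit is 1 − 3.689/15.4 = 76.0%; the profile-likelihood limit is 1 − 1.921/15.4 = 87.5%.

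**The case against.** The strongest reply is that this was an open choice. Protocol and SAP both state it, the SAP ties it to a precedent, and SAP 7.3.3 says "The proposed model is specified prior to performing any interim analysis". An interval conditional on a fixed reference rate is legitimate, the analyses are descriptive, and caution is already advised. That supports keeping the planned interval. It does not make it a 95% CI for VE, and nothing that is certain to be reported carries the control's sampling error, because the Bayesian analysis is optional.

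A second reply is that part of the shortfall comes from the Wald form, which the SAP does not name. This stands: with an exact interval at VE 80%, coverage is close to 95%. At VE 65% a shortfall remains.

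A reader might go further and infer that SAP 7.3.4 prescribes a two-group fit, so that yearly VE, which bears on waning, is misjudged by 2-7 points. The documents do not support this. SAP 6.2.1 gives the variance rule and says Analysis C is done similarly to A. The group names in the zero-case rule sit in a section covering all VE analyses, including periods with a real placebo arm. Under the stated rule, single ZOSTER-049-only years cover about 95%. The 2-7 points show why the wording should be settled; they are not an error in the plan.

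**Conclusion.** The point holds, at modest size. Under the rule in SAP 6.2.1 and protocol 11.7.2, the Analysis A interval is slightly too narrow as a 95% CI for VE. The standard error is about 4-10% too small on the log scale, coverage is about 92-94% (Wald) or 93-95% (exact), and the overall lower limit is about 0.3-1.3 points too high. The shift is about 1-4 points in the assumed strata with 10-25% of the cases. These figures rest on the assumed placebo numbers, follow-up, incidence and VE in the working. They concern sampling error only; bias from a non-concurrent control is a separate matter.

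It would be wrong to infer that the primary conclusion or the 99% precision statement is in doubt. Both survive under every variance rule tried. No error is claimed for Analysis B, whose interval the SAP does not specify, or for the ZOSTER-006/022 years of Analysis C, which use those studies' methods. The wrong cross-reference and the unnamed zero-case lower limit are minor gaps and add nothing to the weight of the point.

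**What to change.** In SAP 6.2.1 and 7.3.4:

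1. State that predicted control cases enter as a fixed offset and not as observed data.
2. For Analysis A, overall and by age stratum, require a 95% interval that also carries the uncertainty of the control rate. Either add to 1/x the delta-method variance of log E from the covariance of the 7.3.3 coefficients, or make the 7.3.2 Bayesian analysis mandatory. On the Bayesian route, use the posterior of the rate; predictive draws of new control cases would bring 1/E back in.
3. Report it beside the prespecified constant-control interval, label the latter as conditional on the historical rate, and base statements about the precision of VE on the interval that carries both sources.
4. Describe and justify the change in the final report, as protocol 11.9 requires.
5. As clean-up, correct the 7.3.4 cross-reference to 7.3.3 and name the lower-limit method for zero HZ/su cases.

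The cost is SAP wording and a small amount of programming, with no new data; the planned point estimates do not change. Limits become slightly wider (overall lower limit about 0.3-1.3 points lower), coverage rises to about 96-97% in sparse cells, and a second interval has to be explained against the Year 2 and Year 4 reports.

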### **6.2.2. Additional Consideration**

In addition to the above mentioned analysis, following additional, sensitivity and subgroup analysis will be performed:-

- ***Frequency of confirmed HZ episodes in ZOSTER-049 on mTVC – LTFU and Control group.***
- ***Distribution of confirmed HZ episodes amongst suspected HZ episodes in ZOSTER-049 on mTVC – LTFU and Control group.***
- ***Distribution of HZAC final decision for each PCR testing results in ZOSTER-049***
- ***Summary of the number of HZ lesion samples not taken on suspected cases in relation to Covid-19 pandemic impact in ZOSTER-049***
- ***Cumulative incidence curve for first or only episode of HZ since one month post dose 2 in ZOSTER-006/022 studies***
- ***Forrest plot: Vaccine efficacy: First or only episode of HZ during ZOSTER-049 study by age strata and overall using Poisson regression method***

- *Forrest plot: Vaccine efficacy: First or only episode of HZ since one month post dose 2 in ZOSTER-006/022 studies by age strata and overall using Poisson regression method*
- *Listing of subjects with severe ‘worst pain’ cases in ZOSTER-049, listing of subjects with confirmed HZ-related complications in ZOSTER-049 (other than PHN), listing of subjects with confirmed HZ related hospitalizations in ZOSTER-049 and listing of subjects with use of pain medications associated with confirmed HZ cases in ZOSTER-049 will be generated on TVC- LTFU and Control group.*

#### 6.2.2.1. **Summary of Covid-19 pandemic impact on suspected sample lesion testing**

*Summary of the number of HZ lesion samples not taken on suspected cases in relation to Covid-19 pandemic impact in ZOSTER-049 will be presented.*

#### 6.2.2.2. **Sensitivity analysis including suspected HZ cases captured in the gap between primary studies and ZOSTER-049 study.**

*In the current calculation of VE for study ZOSTER-049, the suspected HZ cases during the time between the last visit of studies ZOSTER-006/022 and initiation of study ZOSTER-049 (the “gap period”) is not considered as confirmed cases. Per CHMP recommendation, a sensitivity analysis on the primary VE analysis during the entire follow-up period since ZOSTER-006/022 is planned to include potentially confirmed HZ cases during this gap period (Analysis B on mTVC-pooled ZOSTER-006/022 and mTVC-LTFU and Control group).*

*It is known that there are some self-reported suspected cases of HZ during the gap period, but these cases were not able to be confirmed as per the study protocol requirements, hence the true number of confirmed cases is unknown. The planned sensitivity analysis will assume different, yet conservatively high positive rates on the self-reported suspected cases to adequately assess the impact due to potentially confirmed cases. Please refer to Section 7.3.5 for more details*

